9.2 Recording

AE data should be obtained through observation of the subject, from any information volunteered by the subject, or through subject questioning.

All AEs (non-serious and serious) that occur during the course of the study, from the time the subject signs the ICF for the trial until last follow up visit, will be collected and recorded in the e-CRF. Any pre-existing medical conditions or signs/symptoms present in a subject prior to the start of the study (i.e., before informed consent is signed) should be specified in the eCRF. These conditions are considered AEs only if they increase either in frequency or severity once informed consent has been signed. Subsequent to signing an informed consent form, all untoward medical occurrences that occur during the course of the study must be documented on the eCRF. When possible, signs and symptoms indicating a common underlying pathology should be documented as one comprehensive event. Thus, any untoward medical occurrences or unfavorable and unintended signs, symptoms, or diseases that occur in the pretreatment, in treatment, or post treatment period are to be considered AEs and/or SAEs, and consequently recorded and reported as such. Should a non-serious AE become serious, the Investigator will then follow the same reporting procedures as for SAEs.

Each AE will be described by:

- Its duration (start and stop dates).
- Severity grade, as defined in § 9.2.2.
- Assessment of the adverse event relationship to the study treatment
- Any action with study treatment taken as a result of the event.
- Outcome.

All AEs should be followed-up to determine outcome of the reaction. The Investigator should follow up the event until resolution or stabilization of the condition. It is the Investigator's responsibility to assure that the subjects experiencing an AE receive definite treatment for any AE, if required.

Serious Adverse Events:

The Investigator must record all SAEs, including sight-threatening events, occurring at any time during the study regardless of presumed causal relationship, on the Serious Adverse Event form in the eCRF of the Electronic Data Capture (EDC) system within 24 hours of learning of the event; information on the SAE must also be recorded on a specific Non-Carbon Repeat SAE form (included in the Investigator's Site File) and forwarded to Crowsource Drug Safety and Dompé Drug Safety, within 24 hours from first knowledge.

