9.2.2 Severity of Adverse Events

The Investigator will grade the severity of any AE using the definitions in Table 4 below. For each episode, the highest severity grade attained should be reported.

Table 4: Severity of the Adverse Event

Mild	Grade 1 - Does not interfere with subject's usual function (awareness of symptoms or signs, but easily tolerated [acceptable]).
Moderate	Grade 2 - Interferes to some extent with subject's usual function (enough discomfort to interfere with usual activity [disturbing]).
Severe	Grade 3 - Interferes significantly with subject's usual function (incapacity to work or to do usual activities [unacceptable])

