10 STATISTICS

10.1 Study endpoints

Primary safety endpoints are:

- Incidence of treatment emergent adverse events (TEAEs).
TEAEs are defined as an adverse event (AE), which start after first dose of study treatment. These comprise AEs during the treatment and follow-up period.
- Incidence of treatment emergent adverse events during 1st dose schedule (TEAEs Dose 1).
TEAEs Dose 1 are defined as TEAEs, which start after first dose of study treatment and before administration of the first dose at Treatment Day 2.
- Incidence of treatment emergent adverse events during 2nd dose schedule (TEAEs Dose 2).
TEAEs Dose 2 are defined as TEAEs, which start on/after the first dose at Treatment Day 2 and before Follow Up Day 7 (FU1) visit.

Secondary safety endpoints are:

- Incidence of Follow-Up AEs (FUAE)
FUAEs are defined as TEAEs which start on or after Follow Up Day 7 (FU1) visit visit.
- Incidence of ocular TEAEs by eyes.
- Course of ECG parameters ventricular rate, PR interval, QRS duration and QT interval over all visits.
- Course of vital signs parameters systolic and diastolic blood pressure, pulse rate, respiratory rate and body temperature over all visits.
- Changes from baseline in biochemistry parameters over all visits.
Baseline is defined as the Laboratory assessment of Baseline (D-1) Visit
- Changes from baseline in hematology parameters over all visits.
Baseline is defined as the Laboratory assessment of Baseline (D-1) Visit
- Shift in overall interpretation of urinalysis over all visits. Laboratory assessment at Baseline (D-1) Visit is considered as reference for assessing the shift.
- Course of intraocular pressure by eye over all visits.
- Course of visual acuity score by eyes over all visits
The visual acuity score will be derived as the total numbers of letters, which were read correctly at 4 meter plus the total number of letters read at 1 meter as collected on the eCRF page. When 20 or more letters are read at 4 meters the visual acuity score for that eye is recorded as the number of letters correct at 4 meters plus 30. The subject gets credit for the 30 letters at 1 meter even though they did not have to read them. If no letters are read correctly at either 4.0 meters or 1 meter, then the visual acuity score is recorded as "0."
- Course of LogMAR by eyes over all visits.
The logMAR will be derived as – log (Snellen Equivalent result)
- Course of TFBUT by eye over all visits.

- Course of overall NEI score by eye over all visits.

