7.2.6 Primary Safety Endpoints

For this study, the incidence of the following events will serve as primary safety endpoints:

- Treatment emergent adverse events (TEAEs) as defined in section 7.2.8.
- TEAEs during single dose scheme (TEAEs Single Dose):
these comprise all TEAEs, which start after first dose of study treatment and before the date/time of administration of the first dose at Treatment Day 2. In case of missing time, a TEAEs with a start date of the day of D1 Visit will be considered as TEAEs Single Dose.
- TEAEs during multiple dose scheme (TEAEs Multiple Dose):
these comprise all TEAEs during the treatment period, which start after the date/time of first dose of study treatment at D2 Visit. In case of missing time, a TEAEs with a start date on the day of D2 up to D6 Visit will be considered as TEAEs Multiple Dose.

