- An AE is classified as ‘Related’ to Study Treatment if the relationship to study medication recorded as ‘Possible’ or ‘Probable’ or ‘Highly Probable’. An AE will be classified as unrelated to study medication if the relationship to study medication was recorded as ‘None’ or ‘Unlikely’. AEs with missing relationship to study treatment will be counted as ‘Related’ to Study Treatment.
- A Fatal AE is defined as an AE where the outcome is recorded as ‘Fatal’.

These definitions will apply accordingly also for the subsequent sub-classes of AEs.

Non Treatment-emergent adverse events (Non-TEAEs)

A Non-TEAE is defined as any AE, which started before the first administration of study treatment. An AE is considered as Non-TEAE, if the eCRF question “Did the event occur:” was answered with ‘Before Treatment Period’.

Treatment-emergent adverse events (TEAEs)

A treatment-emergent adverse event is defined as an AE that started on or after the date of the First Study Treatment Administration. An AE is considered as TEAE, if the eCRF question “Did the event occurred:” was answered either with ‘During Treatment Period’ or ‘During Follow-Up Period’.

TEAEs in Treatment Period

This is defined as a TEAE (as defined above) that started on or after the date of the First Study Treatment but on or before the D6 Visit. A TEAE in Treatment Period will be identified, if the eCRF question “Did the event occurred:” was answered with ‘During Treatment Period’.

TEAEs in Follow-Up Period (FUAE)

This is defined as a TEAE with a start date on or after D7 Visit. A TEAE will be considered as TEAE in Follow-Up Period, if eCRF question “Did the event occur:” was answered with ‘During Follow-Up Period’.

For listing purposes, treatment day of onset of AE will be derived according to the definition given in section 7.1.

Missing Codes or Incomplete AE start dates:

In the event that coding information will not be available for a specific AE, the event will be presented as ‘Uncoded Event’. However, for final TLFs it is anticipated that all events are coded.

If the eCRF question “Did the event occur:” was not answered, AEs will be classified to subclass Non-TEAE, TEAE in Treatment Period or In Follow-Up Period based on the AE onset date utilizing the definitions given above. If this is not possible, the event will be classified as TEAE in Treatment Period.

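### Treatment-emergent status depends on onset time alone, so an AE that opens before the first drop and worsens on treatment can fall outside the primary TEAE incidence

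*SAP*

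**What the plan says.** Protocol 10.1, repeated in SAP 3.4, sets the definition: "TEAEs are defined as an adverse event (AE), which start after first dose of study treatment". SAP 7.2.8 gives two complementary classes. For Non-TEAEs: "A Non-TEAE is defined as any AE, which started before the first administration of study treatment". For TEAEs: "A treatment-emergent adverse event is defined as an AE that started on or after the date of the First Study Treatment Administration". In practice the eCRF question on when the event occurred (before treatment, during treatment, during follow-up) decides the class. If it is unanswered, "AEs will be classified to subclass Non-TEAE, TEAE in Treatment Period or In Follow-Up Period based on the AE onset date".

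SAP 7.2.6 builds the primary safety endpoint on this: "Treatment emergent adverse events (TEAEs) as defined in section 7.2.8". The single-dose and multiple-dose components in the same section are also split by start time, at the first Day 2 dose.

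Three recording rules in the protocol bear on worsening:

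- Section 9.2 starts collection at consent: "All AEs (non-serious and serious) that occur during the course of the study, from the time the subject signs the ICF".
- Section 9.2 deals with conditions already present before consent: "These conditions are considered AEs only if they increase either in frequency or severity once informed consent has been signed".
- Section 9.2.2 governs grading: "For each episode, the highest severity grade attained should be reported".

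**The concern.** A TEAE definition normally covers two things: events that begin after dosing, and events already present that get worse after dosing. The plan covers only the first. The worsening rule in Protocol 9.2 is anchored to consent, not to the first drop, and applies only to conditions that predate consent. An AE that begins between consent and the first drop and then worsens has no rule that brings it into the treatment-emergent class.

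The window is Day -21 to the Day 1 dose. It includes Day -1, when both eyes have fluorescein instilled and applanation tonometry, so mild ocular complaints shortly before the first drop are plausible.

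TEAE incidence is the primary safety endpoint, and SAP 10.6.1 restricts the tables by SOC and PT, eye, severity, relatedness, seriousness, withdrawal of treatment and study discontinuation to TEAEs. An event judged related because it worsened on treatment could be missing from all of them.

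The gap also sits oddly with the rest of SAP 7.2.8, which is conservative elsewhere. Missing severity counts as severe, missing seriousness as serious, missing relationship as related, and an AE whose timing cannot be classified counts as a TEAE in the treatment period.

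**Working it through.** The plan gives no figure to reproduce here. There is no formal sample size and no inferential analysis. The check is to trace three cases through the rules and then size the effect.

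**Case 1: mild irritation starts on Day -1 and becomes moderate or severe on Day 3.**
1. It starts after consent, so it is an AE (Protocol 9.2).
2. It was not present before consent, so the Protocol 9.2 worsening rule does not apply.
3. If treated as one episode, it is recorded once, at its highest grade (Protocol 9.2.2). Neither document tells the site to open a new record on worsening.
4. It began before the first administration, so it is a Non-TEAE (SAP 7.2.8). The eCRF question leads to the same class, since its answers describe timing only.
5. It is absent from the primary TEAE incidence and from the TEAE tables. A record holding only the peak grade cannot show that the worsening came after dosing.

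**Case 2: an event starts after the single Day 1 drop and worsens on six drops a day from Day 2.**
1. It starts after first dose, so it is a TEAE and counts in the overall primary endpoint and the TEAE tables.
2. It starts before the first Day 2 dose, so it is a single-dose TEAE only (SAP 7.2.6). The multiple-dose component does not see the worsening.
3. SAP 3.6 added AE start times as free text so that events could be assigned to a dose scheme. A start time does not record worsening.

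**Case 3: an event starts on Day 1 before the drop.** It meets the Non-TEAE wording (before first administration) and also the SAP TEAE wording (on or after the date of first treatment). The eCRF answer settles it. If that is blank, the onset-date fallback leads back to the same two overlapping definitions.

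**Size per affected subject**, for a subject with no other TEAE, using the planned arm sizes in Protocol 10.2:
- rhNGF: 1/20 = 5 percentage points
- vehicle: 1/10 = 10 percentage points

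**Chance that it arises at all.** The documents give no rate, so the proportion q of subjects with such an event is assumed. With independent subjects, the probability of at least one in an arm of n is 1 − (1 − q)^n.

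| Assumed q | rhNGF, n = 20 | Vehicle, n = 10 |
|---|---|---|
| 1% | 18% | 10% |
| 2% | 33% | 18% |
| 5% | 64% | 40% |
| 10% | 88% | 65% |

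For example, at q = 2% in the rhNGF arm, 1 − 0.98^20 = 0.33. The expected number of affected rhNGF subjects runs from 0.2 (20 × 0.01) to 2 (20 × 0.10).

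**The case against.** The strongest reply is that worsening is handled elsewhere, so little is lost. Much of this stands as a limit on the consequences.

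- **Examination findings.** Protocol 8.4 to 8.7 and 8.12 require clinically significant worsening first seen during the study to be reported as an AE, for physical examination, vital signs, ECG, laboratory tests and most eye examinations. SAP 7.2.14 adds TFBUT. A sign that first worsens after dosing may therefore produce a new post-dose record. The text does not say that this applies to an AE already open, and it does not cover symptoms.
- **VAS.** Seven ocular symptoms are scored in each eye, and changes in the study eye from Day -1 and from Day 2 pre-dose are primary tolerability endpoints (SAP 7.2.7). Ocular irritation still present at a scheduled score can show there. The VAS does not cover systemic events or times between assessments, and it does not replace AE incidence.
- **Eligibility recheck.** Anterior segment, staining, IOP, TFBUT and general health are checked again at Baseline, which removes many subjects with a meaningful finding before dosing. Symptoms judged minor, and events arising after that check, remain.
- **One record per episode.** Neither document defines an episode, and the eCRF completion instructions are not available. A site might open a second record unprompted. The single-record path is what the text points to, but it is not certain.

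Three stronger readings are tempting, and the documents do not support them. A reader might infer that these events disappear from the report. They do not: SAP 10.6.1 counts all AEs and Non-TEAEs in the overview and lists all AEs, its serious and fatal AE listings are not restricted to TEAEs, and SAP 12 has an unrestricted listing of actions taken. A reader might infer that a Day 1 event that worsens later is lost from the primary endpoint. Only its allocation to a dose scheme is affected. A reader might also infer that the rule makes rhNGF look safer than vehicle. It applies to both arms, one vehicle subject moves incidence twice as far as one rhNGF subject, and no event rates are given.

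**Conclusion.** The point holds. Onset time alone decides treatment-emergent status, and no rule brings in an earlier AE that worsens after dosing. Such an event can be filed as a Non-TEAE at its peak grade, outside the primary TEAE incidence and the tables built on it. The rule can understate TEAE incidence in either arm, by 5 points per affected rhNGF subject and 10 per affected vehicle subject. The direction of any bias between arms is not established.

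This rests on the worsening being kept in the original record, on the affected subject having no other TEAE, and on full planned arms of 20 and 10. The number affected is unknown and probably small in healthy volunteers observed for a short period, and the analysis is descriptive. The change should be made because it concerns a primary endpoint and is cheap, but it does not undermine the trial. The overlap of the two SAP 7.2.8 definitions for AEs starting on Day 1 before dosing needs settling in any case.

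**What to change.** In Protocol 10.1 and SAP 3.4, 7.2.6 and 7.2.8:

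1. Define a TEAE as an AE that starts at or after the first dose, or that starts earlier and, after the first dose, increases in severity or frequency or becomes serious.
2. Apply the same rule at the first Day 2 dose, so that an event worsening on the multiple-dose scheme also counts under that scheme.
3. Have the site record the worsening as a new AE entry with its own date, time, eye and grade.
4. State that the eCRF answer placing an event before treatment does not override the worsening clause.
5. Use one boundary, the time of the first drop, in both SAP 7.2.8 definitions. State how a Day 1 event with no recorded time is classed.

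The cost is revised wording, eCRF completion guidance and minor programming. TEAE incidence may be slightly higher, and some events will have two records, so event counts need a note. For AEs already recorded, a single peak-grade entry cannot show when the worsening happened, so site queries may be needed. They should be limited to AEs that began before the first drop, or between the Day 1 and first Day 2 doses, and were still ongoing at the next boundary. They should be completed before unmasking.

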7.2.9 Secondary Safety Endpoints – ECG

A 12-lead standard ECG tracing with a rhythm strip will be used.

The following ECG measures at each time point were transferred in eCRF:

- Heart rate (ECG Heart Rate)
- PR interval
- QRS duration
- QT interval
- QTc (Fridericia and Bazett corrections)

Clinically significant changes (or a clinically significant worsening) in ECG, which were observed the first time during study will be reported as adverse event.

ECG was assessed at Screening Visit, D-1 0hr, D-1 0.5hr, D-1 2hr, D-1 4hr, D-1 8hr, D1 Pre-Dose, D1 0.5hr, D1 2hr, D1 4hr, D1 8hr, D1 14hr, D2 Pre-Dose, D2 0.5hr, D2 4hr, D2 8hr, D2 10hr, D2 10.5hr, D2 12hr, D3 Pre-Dose, D4 Pre-Dose, D4 4hr, D4 8hr, D5 Pre-Dose, D6 Pre-Dose, D6 4hr, D6 8hr, D6 10hr, D6 10.5hr, D6 12hr, FU1 0hr, FU2 0hr, FU3 0hr and is documented on eCRF Page “ECG”.

For the secondary evaluations the documented parameters ECG Heart Rate (bpm), PR interval (msec), QRS duration (msec), QT interval (msec), QTcB and QTcF (msec) will be described as well as corresponding Changes from Baseline (D-1 0hr).

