The **Treatment Period** starts with the first intake of study medication and ends before the first assessment of the D7 visit. Any assessment before the first intake of study medication is allocated to the **Screening Period**. The **Follow-Up Period** of the study will start with the first assessment on the D7 visit.

Moreover, the Treatment Period is divided into **Treatment Period of the Single Dose Scheme**, which ends before the first intake of study medication on D2 and the **Treatment Period of the Multiple Dose Scheme**, which starts with the first intake of study medication on D2.

If not stated otherwise in subsequent sections, Baseline is defined as the first assessment of the D-1 Visit.

Change from Baseline is defined as the difference between an assessment and the respective first assessment at the Baseline Visit.

Change from Multiple Dose Baseline is defined as the difference between an assessment and the respective Pre-Dose assessment at the D2 Visit.

A **Time-Matched Change from Baseline** is defined as the difference between an assessment and the respective assessment at the corresponding time-point at the Baseline Visit.

Table 2: Study Visits

Scheduled Visit	Scheduled Visit Label	Scheduled Relative Assessment Times within Visit	Comments
Screening Visit	Screening	Before Baseline Visit	Acceptable time window for screening visit: Treatment Day -21 to Treatment Day -2
Baseline Visit	D-1	0 hr 0.5 hr 2 hr 4 hr 8 hr 9 hr 10 hr 11 hr 12 hr 14 hr 16 hr	Acceptable time window: Day before first dose
Treatment Day 1	D1	Pre-Dose 0 hr 0.5 hr 2 hr 4 hr 8 hr 9 hr 10 hr 11 hr 12 hr 14 hr 16 hr	Dosing should occur at 0 hr Time of dosing should be identical to respective time point at baseline visit.
Treatment Day 2	D2	Pre-Dose 0 hr 0.5 hr 2 hr 4 hr 6 hr 8 hr 10 hr 10.5 hr 11 hr 12 hr 13 hr 14 hr 16 hr	Dosing should occur at 0, 2, 4, 6, 8, 10 hr. Time of dosing should be identical to respective time points at baseline visit.

Scheduled Visit	Scheduled Visit Label	Scheduled Relative Assessment Times within Visit	Comments
Treatment Day 3	D3	Pre-Dose 0 hr 2 hr 4 hr 6 hr 8 hr 10 hr	Dosing should occur at 0, 2, 4, 6, 8, 10 hr. Time of dosing should be identical to respective time points at baseline visit.
Treatment Day 4	D4	Pre-Dose 0 hr 2 hr 4 hr 6 hr 8 hr 10 hr	Dosing should occur at 0, 2, 4, 6, 8, 10 hr. Time of dosing should be identical to respective time points at baseline visit.

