7.2.10 Secondary Safety Endpoints – Vital Signs

*Vital Signs evaluation included body weight (in kg with one decimal), and sitting assessments of systolic and diastolic blood pressure and pulse rate as well as respiratory rate and oral body temperature. Blood pressure and pulse rate as well as respiratory rate will be recorded after the subject has rested in the **sitting position** for at least 3 minutes. Blood pressure should be assessed on the same arm for each time of determination using an automated measurement device.*

Body temperature were assessed orally (normal below 37.5°C).

Clinically significant changes (or a clinically significant worsening) in vital signs, which were observed the first time during study will be reported as adverse event.

Vital Signs (with the exception of body weight) were assessed at Screening Visit, D-1 0hr, D-1 0.5hr, D-1 2hr, D-1 4hr, D-1 8hr, D1 0.5hr, D1 2hr, D1 4hr, D1 8hr, D1 14hr, D2 Pre-Dose, D2 0.5hr, D2 4hr, D2 8hr, D2 10hr, D2 10.5hr, D2 12hr, D4 4hr, D4 8hr, D6 4hr, D6 8hr, D6 10hr, D6 10.5hr, D6 12hr and is documented on eCRF Pages “Vital Signs”. Body weight is collected on the same eCRF at Screening Visit only.

For the secondary evaluations the documented parameters systolic and diastolic blood pressure (mmHg), pulse rate (bpm), respiratory rate (breaths/min), as well as oral body temperature (°C) will be described as well as corresponding Changes from Baseline (D-1 0hr).

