7.2.17 Pharmacokinetic Endpoints

Two validated ELISA tests performed at Dompé farmaceutici s.p.a. will be used for PK measurements. The original validated method (ELISA I) will be the same applied to the NGF determination in serum samples taken from studies NGF0112 and NGF0212. A new additional validated ELISA method (ELISA II) will be performed with the intention of improving the sensitivity in the determination of NGF serum levels.

Pharmacokinetics blood samples were taken on Baseline Visit 0 hr, 0.5 hr, 2 hr, 4 hr, 8 hr, 9 hr, 10 hr, 11 hr, 12 hr, 14 hr and 16 hr, for assessment of single dose scheme at D1 Pre-Dose, 0.5 hr, 2 hr, 4 hr, 8 hr, 9 hr, 10 hr, 11 hr, 12 hr, 14 hr and 16 hr, for multiple dose scheme at D2 Pre-Dose, 0.5 hr, 2 hr, 4 hr, 6hr, 8 hr, 9 hr, 10 hr, 10.5hr, 11 hr, 12 hr, 13hr, 14 hr and 16 hr, D3 Pre-Dose, 2 hr, 4 hr, 6 hr, 8 hr, 10 hr, D4 Pre-Dose, D5 Pre-Dose, D6 Pre-Dose, 4 hr, 8 hr, 10 hr, 10.5hr, 11 hr, 12 hr, 13 hr, 14 hr and 16 hr, FU1 0hr, FU2 0 hr and 8 hr, FU3 0hr.

The assessment times are documented on eCRF Pages “Pharmacokinetics – Anti-Therapeutic Antibodies”, the rhNGF serum concentration assessed via both ELISA methods will be provided as external Excel files by Dompé. To maintain masking, these files will be provided for BDRM purposes in a masked manner by utilizing a dummy subject identification. For the final analysis, the Excel Files will contain the correct subject identification number.

The concentration versus time profiles of NGF will be assessed from individual serum samples of all subjects. As a general principle, the nominal assessment times will be used.

For the rhNGF serum levels according to ELISA I and ELISA II time-matched changes from baseline will be presented for the PKS (excluding blood samples at 6 hr, 10.5hr and 13 hr).

For this purposes, values below the limit of detection will be set to a value of 1 pg/ml. However, for listings values below the limit of detection will be presented as “< 32 pg/ml” for ELISA I levels and ‘< 15 pg/ml’ for ELISA II.

A binary variable ‘Presence of rhNGF’ will be derived for each ELISA with ‘No’ indicating a value below the limit of detection and ‘Yes’ indicating a value above the limit of detection.

Beyond the respective rhNGF plasma levels for both ELISA methods, the following parameters will only be investigated for each ELISA method, if the data warrant to do so:

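### ECG and vital-sign changes all use the D-1 0 h value, so at 11 of 27 ECG times and 11 of 19 vital-sign times the within-arm change mixes clock-time effects with any drug effect, although matching D-1 readings exist

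*SAP*

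**What the plan says.** SAP 7.1 sets the default reference: "If not stated otherwise in subsequent sections, Baseline is defined as the first assessment of the D-1 Visit". The ECG section (SAP 7.2.9) follows it: "QTcB and QTcF (msec) will be described as well as corresponding Changes from Baseline (D-1 0hr". So does the vital-signs section (SAP 7.2.10): "oral body temperature (°C) will be described as well as corresponding Changes from Baseline (D-1 0hr".

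The D-1 profile is longer than one reading. For ECG: "ECG was assessed at Screening Visit, D-1 0hr, D-1 0.5hr, D-1 2hr, D-1 4hr, D-1 8hr". For vital signs: "Vital Signs (with the exception of body weight) were assessed at Screening Visit, D-1 0hr, D-1 0.5hr, D-1 2hr, D-1 4hr, D-1 8hr".

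SAP 7.1 also defines a Time-Matched Change from Baseline, which "is defined as the difference between an assessment and the respective assessment at the corresponding time-point at the Baseline Visit". Its only use is for rhNGF concentrations. SAP 7.2.17 says that "time-matched changes from baseline will be presented for the PKS", and Tables 14.6-1.2 and 14.6-2.2 carry it out. The ECG and vital-sign change tables (14.4-1.2 and 14.4-2.2) are plain changes from baseline. SAP 10.7.1 and 10.7.2 also summarise raw values by treatment.

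**The concern.** A post-dose reading at 4 h or 8 h is taken later in the day than the 0 h reference. Protocol 7.6.1 has the first dose of each dosing day given fasted, with breakfast at 2 h and lunch at 5 h. Any ordinary within-day movement in heart rate, QT or QTc, blood pressure or temperature is therefore counted as change from baseline, together with whatever the drug does.

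The design already collects readings that could separate the two. SAP Table 2 asks for dosing at the same clock times as the corresponding D-1 time points, so nominal hours on D-1 and on dosing days are meant to line up.

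At stake is how the within-arm safety change is read. Safety is the primary objective. Protocol 8.6 says that the ECG times were chosen to cover possible rapid absorption and the multiple-dose period. Protocol 2.5 says that no telemetry-type safety pharmacology was done. A within-arm mean change that is partly time of day could be mistaken for a drug signal, or could hide one.

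**Working it through.** The documents give no effect size, SD or sample-size calculation on this point, so there is no planned figure to reproduce. The check is a count, followed by simple algebra.

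**Step 1. Count the times.** Inputs are the schedules in SAP 7.2.9 and 7.2.10, compared with the D-1 times 0, 0.5, 2, 4 and 8 h. Pre-dose and follow-up 0 h readings count as 0 h.

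| | ECG | Vital signs |
|---|---|---|
| D1 | 6 | 5 |
| D2 | 7 | 7 |
| D3 | 1 | 0 |
| D4 | 3 | 2 |
| D5 | 1 | 0 |
| D6 | 6 | 5 |
| FU1 to FU3 | 3 | 0 |
| **Total** | **27** | **19** |
| Already at 0 h | 9 | 1 |
| D-1 match exists, not used | 11 | 11 |
| No D-1 match | 7 | 7 |

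Check: 9 + 11 + 7 = 27 and 1 + 11 + 7 = 19.

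The 11 matchable times are the same in both sets: D1 at 0.5, 2, 4 and 8 h; D2 at 0.5, 4 and 8 h; D4 at 4 and 8 h; D6 at 4 and 8 h (4 + 3 + 2 + 2 = 11). The seven without a match are D1 14 h, and 10, 10.5 and 12 h on each of D2 and D6. For D2 the ECG list reads "D2 8hr, D2 10hr, D2 10.5hr, D2 12hr".

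**Step 2. Place the meals.** Of the 11 times, two (0.5 h on D1 and D2) precede breakfast, one (D1 2 h) coincides with it, and eight (4 and 8 h on four days) follow it. Meal effects can therefore reach eight of the 11 with certainty of order, and clock-time effects can reach all 11.

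**Step 3. What each definition estimates.** Suppose no drug effect, and let d be the shift between 0 h and the later hour, the same on D-1 and on dosing days. For a subject with level s and independent reading errors e:

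- later reading = s + d + e
- D-1 0 h = s + e0, so the planned change = d + (e − e0), with mean d
- D-1 matched hour = s + d + e1, so the time-matched change = e − e1, with mean 0
- rhNGF minus vehicle has mean d − d = 0 under the planned definition and 0 − 0 = 0 under the time-matched one

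**Step 4. Illustration with assumed values.** These inputs are not from the documents: d = 0, 5 or 10 units, between-subject SD 15, within-subject SD 8. The group sizes of 20 and 10 are the protocol's. Simulating 20,000 trials for each d gave:

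| d | rhNGF mean change, D-1 0 h | rhNGF mean change, time-matched | rhNGF − vehicle, D-1 0 h | rhNGF − vehicle, time-matched |
|---|---|---|---|---|
| 0 | −0.01 | 0.00 | 0.01 | 0.04 |
| 5 | 5.00 | 0.03 | 0.04 | 0.03 |
| 10 | 9.98 | 0.00 | −0.01 | 0.02 |

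The standard error of the between-arm difference was about 4.4 under both definitions. This agrees with √(2 × 8² × (1/20 + 1/10)) = √19.2 = 4.38. Time-matching costs no precision here, because each definition subtracts one D-1 reading.

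**The case against.** The strongest reply is that the trial already handles this. The tables are by treatment, so a vehicle column on the same schedule stands beside rhNGF, and Step 3 shows that this contrast is free of the shift. The named endpoint for ECG and vital signs is the course over visits (Protocol 10.1, SAP 3.4), and raw values are tabulated and all data listed. Clinically significant changes are reported as adverse events regardless of these tables. All of this stands. It makes the point one of interpretation, not of validity.

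It does not remove the point. The vehicle group has only 10 subjects, and the plan computes no between-arm difference, so readers must subtract by eye. With complete data, and if raw values are shown at every D-1 hour, the mean matched change is the difference of two tabulated means. Its SD, median and range cannot be recovered that way.

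A reader might infer more than the documents support:

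- *That every change score is affected.* Nine ECG times and one vital-sign time are already at 0 h, and the 0.5 h readings are before breakfast and only half an hour from the reference hour.
- *That the extra D-1 readings go unused.* They serve the raw course; they are only unused as a reference.
- *That the planned change should be replaced.* Changing reference inside one table would put an artificial step between 8 h (matched) and 10 h (unmatched) on D2 and D6.

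**Conclusion.** The point holds for the within-arm change. At 11 of 27 ECG times and 11 of 19 vital-sign times, a usable same-hour D-1 reading is passed over, and any shift between 0 h and that hour passes in full into the reported within-arm mean. At seven further times in each set the clock times also differ, but no D-1 reading exists to correct them.

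A reader might also infer that the rhNGF-versus-vehicle comparison is biased, or that the artefact is large relative to its standard error. Neither is supported. The shift cancels between randomised arms on one schedule, and the documents give neither the size of any within-day effect nor an SD, so any statement in standard errors would be assumption throughout. If the shift is zero, nothing is lost.

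The conclusion assumes that D-1 is a fair picture of the untreated day. For clock time, that rests on the alignment asked for in SAP Table 2. For meals it is unproven: Protocol 7.6.1 gives meal times and the overnight fast for dosing days only. With secondary endpoints, no test and no decision rule, this is a worthwhile, low-cost improvement.

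**What to change.** - In SAP 7.2.9, 7.2.10, 10.7.1 and 10.7.2, add a summary by treatment of the Time-Matched Change from Baseline, as SAP 7.1 defines it, for ECG and for vital signs at the 11 times listed above. Present these as new tables alongside Tables 14.4-1.2 and 14.4-2.2.
- Keep the D-1 0 h change as planned.
- Label the 10, 10.5, 12 and 14 h changes as not time-matched, to be read against the vehicle arm.
- State that time-matching removes meal effects only if D-1 meals followed the dosing-day timetable, and report whether they did.

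The cost is some SAP wording and two extra descriptive tables. No new data are needed, and the protocol endpoint (course over visits) does not change.
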